# 1.1 Background

From the current literature available (*see document Literature Review Table*), it has been suggested that there is a correlation between AF and LA strain values. Existing literature suggests that patients in AF have a reduced LA strain value compared to patients in NSR. However, there are limited studies which also include controlled hypertensive patients despite collecting data regarding blood pressure. Furthermore, the majority of literature reviewed appears to focus on patients that have other comorbidities, and it could be argued that these can affect the parameters measured and analysed. This includes studies involving patients with valvular pathologies such as aortic stenosis and aortic valve replacements as well as studies involving patients with potential structural heart deformations such as those seen with heart failure or following a myocardial infarction. These factors may alter strain patterns and LA size as a result. By listing these factors as exclusion criteria, this study should minimise any external and uncontrollable factors which may affect LA strain value and LA size.

Furthermore, some studies do not have a standardised zero-reference point as some studies used the P wave for NSR and the R wave for AF patients which may cause a discrepancy in results. In this study, it has been agreed that the zero-reference point will be the R wave to create R-R cycles. This is because the P wave is not present in AF and thus cannot be used as a definitive reference point within the AF group. Both groups will have R waves present and therefore, the reference-point can be standardised across all three groups. Additionally, many of the studies reviewed appear to focus on only one LA strain and phase within the cardiac cycle. However, some do include all three. This study will include all three strain values as well as peak atrial longitudinal strain (PALS) values. However, statistical analysis may not be doable for the contractile phase as this is not present in patients with AF. The biggest pitfall that is common to most, if not all, studies reviewed is that the methods used to calculate LA strain were originally designed to measure global longitudinal strain (GLS) of the left ventricle (LV). This study utilises the automated function imaging (AFI) LA atrial strain tool provided by GE Healthcare which is specific to the LA as opposed to GLS methods to track the LV.

The key outcomes from this study will be whether there is a significant difference in atrial strain values between NSR patients, controlled hypertensive patients and patients with either persistent or permanent AF. These electrical changes should correlate with structural changes within the LA as the LA becomes more dilated in AF patients. Furthermore, subtle differences in LA strain values may be observed between patients with paroxysmal atrial fibrillation (PAF), persistent and permanent AF to suggest a decline in atrial strain patterns with a worsening and prolongation of AF.

This will have a significant impact to the general population as AF is the most common arrhythmia. Left atrial enlargement and dilation can occur, either as a cause or complication of AF. However, the detection of this structural change and cardiac remodelling by measuring LA area and volume is often only detected when the patient has been in AF for a prolonged period of time. The utilisation of speckle-tracking echocardiography (STE) and atrial strain measurements may be able to detect subtle changes in LA strain pattern which may occur before any significant cardiac remodelling and LA dilation, and thus serve as an early predictor of AF. This will allow for closer monitoring and the correct administration of anticoagulants. Furthermore, the results from this study will also be generalisable and transferrable and may suggest that LA strain measurements should be more routinely performed during TTEs.

# **1.2 Research Question**

Can measurements of left atrial strain, along with correlating changes in left atrium area and volume size, be used as an early predictor of atrial fibrillation?

# 2. Study Outline

## 2.1 Aims and Objectives

The aims of this research project are split into two sets of comparisons. The first is to determine whether there is a statistically significant difference between atrial strain values in normal sinus rhythm (NSR) patients (control group), to controlled hypertensive patients (disease-control group) and patients with established, chronic AF (disease group). Atrial strain values from these groups will also be compared to left atrium (LA) area and volume to determine correlation. Furthermore, providing there is a significant difference, atrial strain values between AF groups PAF, persistent, and permanent can also be compared to potentiate deterioration of atrial strain.

Null hypothesis: There is no significant difference between the atrial strain measurements in patients with normal sinus rhythm to patients with chronic atrial fibrillation and no correlation between atrial strain measurements and left atrium are and volume size.

Research / alternative hypothesis: There is a statistically significant difference between atrial strain values between patients with normal sinus rhythm and patients with atrial fibrillation and this correlates with changes seen in left atrium area and volume size.

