# **Study Summary**

Study Outline	Atrial fibrillation (AF) is the most prevalent type of arrhythmia within an adult population and is characterised by disorganised, chaotic, electrical activity and thus, ineffective atrial contraction causing irregular ventricular contraction. AF can be categorised into three different groups: paroxysmal, persistent and permanent. The prevalence of AF increases with age and is associated with a range of risk factors including: hypertension, obesity and alcohol consumption. There is a plethora of both cardiac and non-cardiac causes of AF and the cause is not always clear for each patient. Furthermore, causes of AF can also present as the by-product of AF, this increases the difficulty in determining the individual patient's cause of onset. A diagnosis of AF can be incidental as not all patients are symptomatic. If AF goes undetected, this puts the patient at an increased risk of blood clot formation and stroke.
	Patients suspected of having AF are routinely referred for a transthoracic echocardiogram (TTE). It is common for AF patients to have a dilated left atrium (LA). This can be visually confirmed, and the LA area and volume can be measured during a TTE. LA strain measurements are not routinely measured during TTEs but may be able to detect subtle changes in longitudinal strain patterns of the myocardium. By comparing the strain patterns in patients with normal sinus rhythm (control) to those with AF, a scale can be created to suggest and predict whether a patient is likely to develop AF in the future based on these subtle changes before any changes in LA size occur. Furthermore, this can then be further developed to determine whether there are any significant differences in strain patterns between the three AF groups.
Lay Summary	Atrial fibrillation (AF) is the most common type of abnormal heart rhythm. This occurs as the chambers of the heart pump irregularly, often resulting in a fast heart rate and symptoms of irregular pounding and fluttering. There are many risk factors predisposing to AF, however, the cause cannot always be easily determined. Additionally, not all AF patients experience symptoms and consequently, this abnormal rhythm may go undetected and may be discovered accidentally. This is detrimental to patients, as untreated AF patients are at an increased risk of stroke.

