# **1. Introduction**

Atrial fibrillation (AF) is the most prevalent type of arrhythmia within an adult population and is characterised by disorganised, chaotic, electrical activity and thus ineffective atrial contraction causing irregular ventricular contraction (Wyndham, 2000). AF can be categorised into three different groups: paroxysmal, persistent, and permanent. The prevalence of AF increases with age and is associated with, but not limited to, a range of risk factors including hypertension, obesity, and alcohol consumption (Staerk, *et al.*, 2017). There is a plethora of both cardiac and non-cardiac causes of AF and the cause is not always clear for each patient. Furthermore, causes of AF can also present as the by-product of AF, this increases the difficulty in determining the individual patient's cause of onset. A diagnosis of AF can be incidental as not all patients are symptomatic. If AF goes undetected, this puts the patient at an increased risk of blood clot formation and stroke (Markides and Schilling, 2003).

Patients suspected of having AF are routinely referred for a transthoracic echocardiogram (TTE). It is common for AF patients to have a dilated left atrium (LA) and this can be visually confirmed in addition to the LA area and volume measurements (Van De Vegte, et al., 2021). However, as LA measurements are limited to area and volume size, LA strain measurements may be taken but these are not routinely performed during standard TTEs. LA strain is measured using a type of speckle-tracking echocardiography (STE) technique which focuses on the subtle longitudinal changes within the myocardium to analyse myocardial deformation (Gan, et al., 2018). Strain imaging of the LA produces three functional strain values (contractile, conduit and reservoir) which correspond to different stages of the cardiac cycle (Jarasunas, et al., 2018). As patients in AF lack normal atrial contraction and have a loss of atrial kick, it is expected that the contractile strain, associated with LA contraction, is not present. However, the conduit and reservoir functions can still be compared across all three study groups to create a scale to suggest and predict whether a patient is likely to develop AF in the future; prior to any changes in LA size. Furthermore, this can then be further compared to determine whether there are any significant differences in strain patterns between the different groups of AF.

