#### 2.2.6 Statistical Analysis Plan

Continuous data normality will be assessed utilising the Shapiro-Wilk test. Nonparametric data will be analysed via Mann-Whitney U tests and Kruskal-Wallis oneway ANOVA tests. If data shows a normal distribution, to compare the LA strain values between the control (NSR) and disease (AF) groups an independent T-test can be performed; this will establish whether there is an initial statistically significant difference between the two. Following this, to compare the mean strain values for each phase between the three groups, a one-way ANOVA must be performed. A one-way ANOVA can also be performed to determine any significant differences between the strain values between AF groups. These data analysis methods will also be repeated to analyse LA area and volume. To assess whether LA area and volume size correlate with LA strain, a Pearson correlation coefficient must also be performed. Furthermore, to determine whether LA strain may be used as an early predictor of AF, linear regression models must be adapted. For categorical data, such as gender, chisquared tests will be performed to determine any significant difference between groups. All statistical tests will be performed using the Prism GraphPad software.

It is expected that there will be a significant difference in strain values between NSR and AF participants. It is also expected that an increase in LA area and volume size will correlate with a decrease in LA strain values.

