#### 2.3 Study Outcomes

The key outcomes from this study will be whether there is a significant difference in atrial strain values between NSR patients, controlled hypertensive patients and patients with either persistent or permanent AF. These electrical changes should correlate with structural changes within the LA as the LA becomes more dilated in AF patients. Furthermore, subtle differences in LA strain values may be observed between patients with PAF, persistent and permanent AF to suggest a decline in atrial strain patterns with a worsening and prolongation of AF.

This will have a significant impact to the general population as AF is the most common arrhythmia. Left atrial enlargement and dilation can occur, either as a cause or complication of AF. However, the detection of this structural change and cardiac remodelling by measuring LA area and volume is often only detected when the patient has been in AF for a prolonged period. The utilisation of speckle-tracking echocardiography (STE) and atrial strain measurements may be able to detect subtle changes in LA strain pattern which may occur before any significant cardiac remodelling and LA dilation, and thus serve as an early predictor of AF. This will allow for closer monitoring and the correct administration of anticoagulants.

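### The rationale is that strain may fall before the left atrium enlarges, but no specified analysis compares strain at equal or normal LA size, so a positive result would not separate this from strain tracking size

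*Combined protocol and SAP*

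**What the plan says.** The premise appears four times. The Study Summary wants a scale that predicts future AF "based on these subtle changes before any changes in LA size occur". The Introduction repeats the idea ("prior to any changes in LA size"). Sections 1.1 and 2.3 say strain may "detect subtle changes in LA strain pattern which may occur before any significant cardiac remodelling and LA dilation", and 1.1 gives this as the reason it would be an early predictor.

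The research question in 1.2 already ties strain to size: can strain, "along with correlating changes in left atrium area and volume size, be used as an early predictor of atrial fibrillation"? The alternative hypothesis in 2.1 requires a strain difference between sinus rhythm (NSR) and AF and adds that "this correlates with changes seen in left atrium area and volume size". The null hypothesis is no difference and no correlation.

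Section 2.2.6 plans:
- a t-test of strain, NSR against AF, and a one-way ANOVA across the three groups, or rank tests if the data are not normal;
- the same tests, run separately, on LA area and volume;
- a correlation: "To assess whether LA area and volume size correlate with LA strain, a Pearson correlation coefficient must also be performed";
- linear regression for the early-predictor question, with no outcome, predictor or covariate named.

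It also states the expectation that larger atria will go with lower strain. Each participant has one scan (2.2.2) and there is no follow-up (2.4). The disease group has established persistent or permanent AF (2.1, 2.2.4).

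**The concern.** To support the premise, the data must show lower strain in people whose atria are not enlarged. The specified tests show something else: whether strain differs between groups whose LA size is expected to differ, and whether strain and size move together. The Introduction and 1.1 expect dilated atria in AF, so the NSR-AF contrast is largely small atria against large ones. Strain that carried no information beyond size would give the same findings.

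This matters because LA area and volume are already measured routinely (2.2), and 1.1 anticipates that the results may support measuring strain routinely as well. That recommendation depends on strain adding something to size, which no specified analysis examines.

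**Working it through.** **1. The plan's own figure.** From 2.2.5, the difference is 4.0 and the SD 7.5, with three groups, alpha 0.05 and power 0.85. With two means 4.0 apart and the third midway, f = (4.0/7.5) × √(1/6) = 0.5333 × 0.4082 = 0.2177. This is the value in the Appendix Figure 1 output. Then λ = f²N = 0.2177324² × 234 = 11.093, critical F(2, 231) = 3.035 and power = 0.851. The total of 234 reproduces exactly, so the sample-size arithmetic is not in question. The f used implies a hypertensive mean 4.0/2 = 2 points from NSR. That agrees with the Introduction, which expects this group to lie between the other two.

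**2. What the specified tests show if strain only follows size.** The documents give no LA volumes and no strain-size slope, so all inputs here are assumptions. The model has 78 per group; LA volume with SD 14/15/22 mL in NSR/hypertension/AF; strain = constant + slope × volume + error with SD 6.5; and no group effect at given volume.

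| Mean LA volume (mL) | Slope (points/mL) | t-test, ANOVA and negative correlation all significant |
|---|---|---|
| 50/56/80 | −0.2 | 99.7% |
| 50/56/80 | −0.1 | about 71% |
| 50/56/80 | −0.05 | about 19% |
| 50/53/65 | −0.2 | about 61% |
| 50/53/65 | −0.1 | about 20% |
| 50/53/60 | −0.2 | about 29% |

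The first row implies a size-driven NSR-AF difference of 30 × 0.2 = 6 points, which is 1.5 times the protocol's 4.0, so it lies at the high end. The NSR-hypertension comparison adjusted for LA volume is significant in about 5% of runs, its nominal level.

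A second model works in SD units, with the AF-NSR size gap at 0.5 to 1.5 SD and the within-group correlation at −0.3 to −0.7. Both parts of the alternative hypothesis (t-test and correlation) are met in 16% to 100% of runs. A test of group adjusted for size rejects in 4% to 6%.

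**3. The converse.** Suppose strain differs by 4.0/7.5 SD while size neither differs between groups nor correlates with strain. The NSR-AF t-test is then positive in 91% of runs, but both parts of the alternative hypothesis are met in only about 4%. The hypothesis would usually fail in a case that favours strain as a marker separate from size. This needs a true correlation of zero; at −0.3 within groups both parts are met in about 92%.

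**4. What a size-adjusted comparison could detect.** Use the first-row model, NSR against hypertension. The mean within-group variance of volume is (14² + 15²)/2 = 210.5 and the mean volume gap is 6 mL.

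SE = 6.5 × √(2/n + 6²/(2n × 210.5))

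- n = 78: 6.5 × √(0.02564 + 0.00110) = 1.06 points, so the 95% interval is about ±2.1.
- n = 40 (assumed size of a normal-LA subset): 6.5 × √(0.05 + 0.00214) = 1.48 points, so about ±3.0.

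| True size-independent deficit | Power, 78 per group | Power, 40 per group |
|---|---|---|
| 4 points | about 96% | not needed here |
| 2 points (midway value from step 1) | about 46% | about 26% |
| 1 point | about 16% | about 10% |

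**The case against.** **The linear regression might include LA size.** It might. Section 2.2.6 names no outcome or covariate, so the plan neither includes nor excludes it. The fair criticism is that the model is unspecified. Without LA size it adds nothing: a simple regression of NSR/AF status on strain gives the same p-value as the equal-variance t-test, and a simple regression of strain on size gives the same p-value as the Pearson test.

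**The three-group tests would show low strain with similar LA size in hypertension.** That pattern would be visible. But one significant and one non-significant separate test do not show a difference at equal size, and no such comparison is planned.

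**The premise is hedged, and the formal aims are only difference and correlation.** This is true: 1.1 and 2.3 say what may occur, and the stated aims are tested. The gap lies between those aims and the interpretation the text prepares, so it is settled with one analysis and some wording.

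**One scan cannot show time order.** Agreed, and no analysis of these data will. Reduced strain at a given LA size can still be examined with them.

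A reader might go further and infer that the alternative hypothesis asks for the opposite of the premise. It does not. A cross-sectional correlation is also what one would see if strain fell first and size followed. It fails to discriminate, but it does not contradict the premise.

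**Conclusion.** The point stands as a gap between rationale and analysis. As specified, a positive study would be compatible with strain falling before dilation and with strain tracking size, and nothing in 2.2.6 would separate them. That follows from the tests chosen and does not rest on the simulation.

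How often a size-only mechanism would satisfy the planned tests does rest on assumptions: about 19% to 99.7% across the slopes and size gaps tried. Two stronger inferences are not supported. One is that the planned tests will be positive whenever strain tracks size; the rate falls to about a fifth with weak slopes or smaller gaps. The other is that a non-significant size-adjusted result would show strain to be merely parallel to size. With about 46% power at the 2-point difference implied by the protocol's own f, such a result would leave the question open.

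**What to change.** In 2.2.6, prespecify a comparison of strain between NSR and controlled-hypertensive participants, both in sinus rhythm, with LA volume as a covariate. Add a supportive repeat in participants whose LA volume is within the department's normal range. Report each as an estimate with a 95% confidence interval.

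Tie the early-change wording in 2.3, and the same text in 1.1, to that estimate:
- If the interval excludes zero in the direction of lower strain, conclude that strain was reduced at a given (or normal) LA size, and claim no time sequence.
- If it includes zero, conclude that a size-independent difference was not shown. Do not conclude that strain merely parallels size.

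The cost is one regression, one subset analysis and some rewording. It needs no extra participants, scans or visits, because strain and LA volume are already collected on everyone. The drawbacks are the limited precision shown above, especially in the normal-size subset, and a conclusion that may be less favourable than the present text.

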#### 2.2 Method

Patient selection:

Potential candidates for this study will have been referred for a TTE by a healthcare professional. The referrals will be reviewed and if the patient meets the initial eligibility criteria, they will be considered as part of this study. The initial eligibility criteria consist of being over the age of 50 (although patients will be age-matched across the three groups) and falling within the control (normal sinus rhythm), disease-control (controlled hypertension) or disease groups (chronic AF).

Data collection:

The images obtained from the TTE scan will be stored on the ultrasound machine as well as the picture archiving systems (PACS) on the computer. The measurements to be compared are:

- Left atrium area
- Left atrium volume
- Left atrium strain measurement and analysis using the R wave

The first two measurements are routinely performed during TTEs, but atrial strain measurements are not routinely performed. This additional measurement will not affect or delay the TTE results and report from being sent back to the referrer or delay any further correspondences with other healthcare professionals. Atrial strain measurements will be conducted using the AFI LA atrial strain tool provided by GE Healthcare. These three measurements will be compared across the three groups and tested for a statistically significant difference. Providing that there is a significant

difference, particularly between the control and disease groups, a subsequent comparison will be conducted between the three groups of AF using the existing data.

#### 2.2.1 Study Type

Single centre case-control study, quantitative and a prospective study.

#### 2.2.2 Study Overview

- Study design quantitative, observational, case-control study.
- Patients will be assigned to one of three groups: control group (normal sinus rhythm), disease-control group (controlled hypertension) and disease group (chronic atrial fibrillation).
- Patients will be required to visit the department on one occasion. This will be as part of either a routine or urgent referral for a transthoracic echocardiogram (TTE).
- TTEs are stored on both the ultrasound machines and computer picture archiving systems (PACS). Measurements can be taken on either the ultrasound machine or on the PACS following the patient's scan. The data obtained from these scans that will be utilised include patient demographics, heart rate and rhythm, LA area and volume measurements as well as LA strain measurements. This will be pseudo-anonymised using two Excel spreadsheets and the document will be password encrypted on a NHS OneDrive account
- Study site: within the Cardio-Respiratory department at Withybush General Hospital, there are five sonographers. This creates a throughput of approximately 60 TTE scans per week. With an expected data collection period of five months, this would equate to approximately 1200 outpatient scans factoring in annual leave and sickness. Additionally, inpatient scans can boost this number, but is dependent on current demand.

